studies by Hardaway et al evaluating fibrinolytic therapy for treatment of ARDS used urokinase and streptokinase, the more contemporary approach to thrombolytic therapy involves the use of tissue-type plasminogen activator (tPA) due to higher efficacy of clot lysis with comparable bleeding risk to the other fibrinolytic agents.

Hypothesis:

We hypothesize that administration of tPA to patients with COVID-19 associated severe ARDS will improve pulmonary gas exchange and oxygenation via a decrease in pulmonary vascular microthrombi.

Study Design:

This is a Phase IIa clinical trial, open label, with a modified stepped-wedge design, testing systemic administration of fibrinolytic therapy with alteplase (tPA) versus standard of care for patients infected with COVID-19 resulting in severe respiratory failure. The design is a rapidly adaptive, pragmatic clinical trial, with 3 interim analyses and 1 final look at the data. Pre-planned adaptations described below will be contemplated at each interim analysis or earlier if recommended by the Data Safety Monitoring Board (DSMB).

Inclusion Criteria: We will include adult patients ages 18-75 years old with known or suspected COVID-19 infection with a PaO₂/FiO₂ ratio < 150 or inferred PaO₂/FiO₂ ratio from SpO₂ if ABG is unavailable (Table) persisting for > 4 hours despite optimal mechanical ventilation management according to each institution's ventilation protocols, and a neurological exam without focal signs or new deficits at time of enrollment (if patient is on paralytics, patient has been aroused sufficiently to allow a neurological examination to exclude new focal deficits or has MRI/CT scan in the last 4.5 hours with no evidence of stroke. Finally, patients must be on the ventilator for ≤10 days to be eligible. Based on experience with critically ill patients, longer ventilation time may be associated with increased risk of bleeding. Patients will be enrolled based on clinical features, without consideration of language (using hospital interpreters and translated consent), race/ethnicity, or gender. A neurological exam or CT/MRI scan to demonstrate no evidence of an acute stroke is needed due to a recent case-report of large-vessel stroke as a presenting feature of COVID-19 in young individuals.⁴⁴

SPO2	FIO2														
	0.3	0.35	0.4	0.45	0.5	0.55	0.6	0.65	0.7	0.75	0.8	0.85	0.9	0.95	1
80%	148	127	111	98	89	81	74	68	63	59	55	52	49	47	44
81%	151	129	113	101	91	82	76	70	65	60	57	53	50	48	45

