Additional two tubes (total volume up to 8.0mL) of blood will be drawn at each timepoint to be processed in the research lab.

Thrombo Therapeutics, Inc. is not involved in this study. TPA-challenged TEG assay is used for research purposes only. The data from this test is not accessible for the clinical care providers and

does not affect the patient care. We are using this assay to study the clot sensitivity and as a marker for hypercoagulability. The results of tPA-challenged TEG assay will not be used for any clinical decision or research subject assignment. At the moment there is no plan to submit tPA-challenged TEG data to the FDA.

Follow-up:

Patients will be followed to death or discharge up to 28 days. Laboratory measurements related to the research study, however, will end at day 7 after randomization.

Outcomes:

Primary Outcome: PaO₂/FiO₂ improvement from pre-to-post intervention at 48 hours post randomization. Ideally, the PaO₂/FiO₂ will be measured with the patient in the same prone/supine position as in baseline, as change in positions may artificially reduce the improvement attributable to the study drug. However, given the pragmatic nature of the trial, the prone/supine position will be determined by the attending physician, in which case, we will use as an outcome the PaO₂/FiO₂ closest to the 48 hours obtained prior to the change in position as the outcome.

Secondary outcomes (assessed 48 hours after randomization or as indicated):

- PaO₂/FiO₂ improvement from pre-to-post intervention at **24 hours** post randomization.
- Amendment Nov 5, 2020: add the outcome "Decrease in ventilatory dead space as estimated by the ventilatory ratio at **48 hours.**" Based on a recent study, (Orfanos S, El Hussein I, Nahass T, et al. Observational study of the use of recombinant tissue-type plasminogen activator in COVID-19 shows a decrease in physiological dead space. ERJ Open Res 2020; 6: 00455-2020), this outcome seems to appropriate to assess the efficacy of the intervention. As most of the subjects do not have capnography data, we will be using the ventilatory ratio, which has been shown to correlate well with dead space.
- Achievement of PaO₂/FiO₂ ≥ 200 or 50% increase in PaO₂/FiO₂ (whatever is lower)
- National Early Warning Score (NEWS2): based on 7 clinical variables (respiration rate, oxygen saturation, any supplemental oxygen, temperature, systolic blood pressure, heart rate, level of consciousness).

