- 2) If at the end of the second intervention deployment (total of 20 patients randomized), the primary outcome improves (PaO₂/FiO₂ ratio at 48 hours) by $\geq 20\%$, or the secondary outcomes PaO₂/FiO₂ ratio at 24 hours improves $\geq 20\%$, or dead space decreases by 15%, or ICU- or ventilator-free days continue to exhibit a positive response (at least 2 days difference), we will modify the mode of administration of the second dose of tPA as follows: following the 50mg tPA bolus, we will initiate a drip of 2 mg/hr tPA over the ensuing 24 hours (total 48 mg infusion) accompanied by an infusion of 500 U/hour heparin during the tPA drip. After this, heparin dose will be increased slowly to maintain a PTT between 60 and 80 sec, titrated per attending's discretion. Interim analyses will be conducted as planned above, and submitted expeditiously to the DSMB, IRB and FDA for approval, yet enrollment will continue while these agencies deliberate and their feedback is received.

See above for the rationale for the tPA50+drip.

Statistical analysis (see attached Statistical Analysis Plan):

All analyses will be conducted initially as an intent-to-treat (patients are analyzed in the group they were randomized to), followed by an as-treated analysis. We will use linear mixed models (continuous outcomes, appropriate transformations if residuals normality departure is detected) or generalized estimating equations (categorical outcomes) to account for intra-hospital cluster effects and repeated measures, with FINAL (OVERALL) significance at $p < 0.05$ (two-tailed tests). If the groups are not comparable, we will compare relative (as opposed to absolute improvement over baseline (with patients as their own controls) to minimize the effect of baseline disparities. In addition, as the sample permits, we will adjust for confounders using a single propensity score adjustor in an inverse probability weighting approach. In addition, we will compare the "dose" of the intervention (i.e., how much of the treatment the patient received) as the effect of interest. The pre-planned final comparisons include within group (improvement over baseline) and between groups, all two-tailed with significance declared according to the alpha defined above by the Pocock spending method.

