### 3.2. Sample size

We anticipate that each of the five centers will enroll 8-12 patients. Sample size and power Analysis was conducted using Pass, vs 14.0 (NCSS, LLC, Kaysville, Utah, USA) and focused on the primary outcome as defined above.

Sample size assumptions:

- power=80%, confidence=95%, and 4 sequential tests(3 interim+1 final), using the Pocock spending function to determine test boundaries,
- potential improvement assumptions based on a previous study 40 with appropriate(e.g., Denver) altitude correction as well as mean baseline PaO2/FiO2=149 with an overestimated standard deviation of 100,
- design effect=1.12 due to the study's multicenter nature (intra-class correlation coefficient=0.03, average cluster=5);
- ~20% inflation to account for premature death

---

 Urbaniak, G. C., & Plous, S. (2013). Research Randomizer (Version 4.0) [Computer software]. Retrieved on April 10, 2020, at <http://www.randomizer.org/>

A sample size of 50 (25 in each intervention group and 25 in the control group) patients detects a >70% improvement in PaO2/FiO2 between intervention groups (both tPA50 and tPA 50 plus drip) and controls, and >91% improvement in PaO2/FiO2 between intervention tPA 50 plus drip) and controls. Recruitment will assume at least 30% increase to account for refusal or inability to consent.

**Consent: We anticipate consenting enough patients to result in 50 eligible patients, thus we plan on a max of 60, to be re-evaluated during each of the interim analyses. LAR, as defined by the state and institutions legislation/policies, will be able to consent.**

The table below shows the details of the interim analyses with the Pocock spending method:

Look	N of Patients	Lower Bndry	Upper Bndry	Nominal Alpha	Inc Alpha	Total Alpha	Inc Power	Total Power
1	10	-2.43798	2.43798	0.015	0.015	0.015	0.18976	0.190
2	20	-2.42677	2.42677	0.015	0.011	0.026	0.25179	0.442
3	30	-2.41014	2.41014	0.016	0.009	0.035	0.21191	0.653
4	50	-2.39658	2.39658	0.017	0.008	0.043	0.14655	0.800

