### 5.2. Eligibility:

**Inclusion Criteria:** We will include patients ages 18 to 75 years, with known or suspected COVID-19 infection, with a neurological examination without focal signs or new deficits at time of enrollment (if patient is on paralytics, the patient has been aroused sufficiently to allow a neurological examination to exclude new focal deficits or has MRI/CT scan in the last 4.5 hours with no evidence of stroke), with a PaO2/FiO2 ratio < 150 (at sea level or adjusted for altitude) persisting for longer than 4 hours despite maximal mechanical ventilation management according to each institution's ventilation protocols (FiO2 of 60% or more and PEEP greater than or equal to 10cmH2O). If obtaining arterial blood gas is not possible, we will infer the PaO2/FiO2 ratio from percent saturation of hemoglobin with oxygen as measured by pulse oximetry (SpO2), using the nonlinear imputation developed by the National Heart, Lung and Blood Institute (NHLBI) PETAL (Prevention and Early Treatment of Acute Lung Injury) Network Collaborators A neurological exam or CT/MRI scan to demonstrate no evidence of an acute stroke is needed due to recent reports of large-vessel stroke as a presenting feature of COVID-19 in young individuals.

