### 6.4. Outcomes comparison:

All analyses will be conducted initially as an intent-to-treat (patients are analyzed in the group they were randomized to), followed by an as-treated analysis. The primary outcome will be assessed within group and between groups. Differences in the primary outcome will be assessed using linear mixed models, with appropriate transformations if normality departure of residuals is detected. Linear mixed models allows us to adjust for potential confounders detected in the comparison of the groups at baseline using inverse probability weighting by a propensity score, the covariance structure, the repeated measures and the intra-hospital correlation (as this is a multicenter study). In addition, it tolerates missing observations. We will also compare percent change over baseline, using t-tests with the appropriate adjustment for heteroscedasticity if needed. Categorical outcomes will be compared using generalized estimating equations to account for confounders (as above), covariance structure and intra-hospital correlation. In addition, we will compare the “dose” of the intervention (i.e., how much of the treatment the patient received) as the effect of interest, as premature death is, unfortunately, expected. Survival analysis with inverse probability weighted Cox proportional hazards model and robust sandwich variance estimate with clustering for hospitals will be used for mortality and for survivor-bias outcomes censoring for death (e.g., thrombotic complication). As all outcomes are in-hospital, loss to follow-up is not likely. The pre-planned comparisons include within group (improvement over baseline) and between groups, all two-tailed with significance declared as defined by the Pocock spending method.

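### Within-group improvement over baseline is listed among the comparisons declared significant, although patients are selected on a low PaO₂/FiO₂ and a within-arm rise is not evidence of a tPA effect

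*SAP*

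**What the plan says.** The primary outcome in both documents is PaO₂/FiO₂ "improvement from pre-to-post intervention at 48 hours post randomization", a change from baseline. SAP 6.4 adds: "The primary outcome will be assessed within group and between groups". Later in the same section: "The pre-planned comparisons include within group (improvement over baseline) and between groups", "all two-tailed with significance declared as defined by the Pocock spending method". The Protocol, under Statistical analysis, repeats the rule: "The pre-planned final comparisons include within group (improvement over baseline) and between groups".

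The Protocol's inclusion criteria admit adults "with known or suspected COVID-19 infection with a PaO₂/FiO₂ ratio < 150". SAP 5.2 has the same limit, "persisting for longer than 4 hours despite maximal mechanical ventilation management".

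Two decision rules use the primary outcome without naming a comparison:

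- **Efficacy stopping** (Protocol stopping criteria; SAP 3.3) requires an adjusted p-value on the primary outcome and on at least one secondary outcome.
- **Adaptation after 20 randomised patients** (Protocol, Adaptive design; SAP 3.1 and 3.4) turns on whether 48-hour PaO₂/FiO₂ improves by at least 50% or at least 20%.

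Neither document mentions regression to the mean or natural recovery.

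**The concern.** Patients enter because the variable that later serves as the outcome is low. Part of a low reading is within-patient fluctuation, so the next reading tends to be higher whatever is given. Recovery, proning and ventilator changes can add to that. A pre-to-post test within one arm cannot separate any of this from tPA.

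Because SAP 6.4 and the Protocol put that test among the comparisons on which significance is declared, a report could follow the plan to the letter and announce a significant improvement on the primary outcome with tPA no better than control. The unnamed comparator in the stopping and adaptation rules widens the exposure: as written, a within-arm p-value or a within-arm percentage rise could be read as meeting them.

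**Working it through.** **1. The plan's own figure.** SAP 3.2 assumes "power=80%, confidence=95%, and 4 sequential tests(3 interim+1 final), using the Pocock spending function to determine test boundaries", baseline mean 149, SD 100, design effect 1.12, about 20% inflation for death, and 25 versus 25 patients for a 70% difference.

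- Effective n per arm = 25 × 0.8 / 1.12 = 17.9.
- Difference = 0.70 × 149 = 104.3.
- Drift = 104.3 / (100 × √(2/17.9)) = 3.12.
- Simulating the four SAP boundaries at 10, 20, 30 and 50 patients gives 79.4% power, against 80% stated.

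The sample size therefore rests on the between-group difference alone. The within-group test plays no part in it.

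**2. Inputs for the within-group test with no drug effect.**

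- From the documents: entry limit 150. The level is 0.0165, between the SAP's nominal 0.016 and 0.017 at looks 3 and 4; half of it, 0.8%, lies in the direction of improvement.
- Patients per arm: 20 is the pooled tPA group after deaths (25 × 0.8). With equal allocation, SAP 3.1 gives about 5 on tPA50 at the first look, 10 on tPA50 by the second, and 15 on tPA50 plus drip at the end.
- Assumed, because the documents do not give them: candidate mean μ 110–180, SD σ 40–60, baseline-to-48-hour correlation ρ 0.5–0.9, bivariate normal values, paired t-test.

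**3. Formulas.** Let b = (150 − μ)/σ and λ = φ(b)/Φ(b).

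- Mean at entry = μ − σλ.
- Expected rise = (1 − ρ)σλ.
- SD of change = σ√[(1 − ρ)²(1 − bλ − λ²) + 1 − ρ²].
- Noncentrality δ = √n × rise / SD of change. The false-improvement rate is the chance that a noncentral t with n − 1 degrees of freedom exceeds the critical value (2.63 at n = 20).

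Example with μ = 180, σ = 40, ρ = 0.5:

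- b = −0.75 and λ = 0.301/0.227 = 1.329.
- Mean at entry = 180 − 53.2 = 126.8.
- Rise = 0.5 × 40 × 1.329 = 26.6, or 21%.
- 1 − bλ − λ² = 0.231, so SD of change = 40√(0.25 × 0.231 + 0.75) = 35.9.
- δ = 26.6 × √20 / 35.9 = 3.31, giving 74%.

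**4. Results at n = 20.**

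| μ | σ | ρ | Rise (mmHg) | False improvement |
|---|---|---|---|---|
| 110 | 40 | 0.9 | 1.2 | 1.7% |
| 130 | 40 | 0.7 | 6.1 | 6% |
| 150 | 40 | 0.5 | 16.0 | 27% |
| 180 | 40 | 0.9 | 5.3 | 13% |
| 180 | 60 | 0.5 | 34.2 | 58% |
| 180 | 40 | 0.5 | 26.6 | 74% |

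For the last row the same formula gives 10% at n = 5, 34% at n = 10 and 57% at n = 15.

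Simulation over the grid, with implausibly low baselines excluded, gives about 1% to 76% at n = 20 and maxima of about 11%, 32% and 56% at n = 5, 10 and 15. The two methods agree within a few points. In the same runs the between-group test rejected in 1.3–2.1%, against 1.65% nominal.

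**5. Two checks on the model.**

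- *Persistence beyond 4 hours.* Requiring a second value below 150 about 4 hours earlier did not remove the effect. At μ = 130, σ = 40, ρ = 0.5, n = 25 and level 0.017, the rate went from 14% to 19%.
- *Recovery.* In that population (μ = 130, σ = 40, persistence required, n = 25), an assumed natural recovery of 15 mmHg gave 84–98% over ρ = 0.5–0.9, and 30 mmHg gave about 100%.

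**6. Link to the adaptation rule.** With no drug effect, ρ = 0.5–0.7 and μ = 130–180, the simulated mean rise is 6–33 mmHg, or 5–29% of baseline. The upper part of that range passes a 20% threshold if the threshold is read within arm.

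**The case against.** The strongest reply is that the trial has what it needs. Each stage has a randomised concurrent control, a between-group test is pre-planned, and the sample size and Pocock table are built on it. SAP 3.2 also questions rigid cutoffs and promises effect sizes with confidence intervals for all comparisons. Within-group testing covers controls too, so a common drift would be visible. All of this stands, and it confines the fault to the status of one p-value. It does not justify declaring significance on an uncontrolled contrast.

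The size is also open to challenge. The high rates need a candidate mean well above the entry limit and a modest correlation. At ρ = 0.9 and means of 130–180 the rate is about 2–13%; at a mean of 110 it is about 1–3%; at n = 5 it is at most about 11%. The planned mixed model is not a paired t-test. These points stand: the figures show what is possible, not what is likely.

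Three stronger readings are tempting, and the documents do not support them.

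- *That selection guarantees a rise in both arms.* SAP 6.4 expects premature deaths, and deterioration could offset regression.
- *That the sponsor has already argued efficacy from a within-arm rise.* The November 2020 rationale in the Protocol reports a 24-hour improvement, lost over the next 24 hours, without saying whether it was within arm or against control. It was used to choose a mode of administration.
- *That the adaptation rule is a within-arm rule.* No comparator is named, and the limb on ICU- or ventilator-free days speaks of a difference, which suggests a comparison with control. The text is ambiguous rather than wrong on this.

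**Conclusion.** Wrong as written, in one respect. Both documents give a within-group p-value on the primary outcome the standing of a declared result, at the same Pocock levels as the randomised contrast, for an outcome on which patients were selected. A significant rise within an arm would not be evidence that tPA works.

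The size cannot be fixed from the documents. It runs from close to nominal to most arms under the assumptions above, and natural recovery could matter more than regression to the mean. The conclusion does not depend on where in that range the truth lies, because the contrast is uncontrolled in every case. The between-group comparison is valid on this point.

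**What to change.** 1. In SAP 6.4 and the Protocol's statistical analysis section, remove within-group tests from the comparisons on which significance is declared. Report change within each arm, including control, with a confidence interval and label it descriptive.
2. State that efficacy is declared only on tPA minus concurrent control in 48-hour PaO₂/FiO₂, adjusted for baseline PaO₂/FiO₂.
3. In the efficacy stopping rule (Protocol stopping criteria; SAP 3.3), state that the adjusted p-value is that of the comparison with concurrent control.
4. In the adaptation rules (Protocol, Adaptive design; SAP 3.1 and 3.4), state that improvement means the difference from concurrent control.

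The core change is one sentence in each document; items 3 and 4 add a clause wherever those rules appear. The sample size of 50 and the stated 80% power are unaffected, because they already rest on the between-group difference. No descriptive information is lost.

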### 6.5. Pre-planned subgroup analyses

We anticipate the following subgroup analyses, which will assist in determining whether there is a subgroup of patients for whom the intervention is more beneficial/harmful.

- Baseline PaO2/FiO2 <100 and <50
- Hemodynamic instability with vasopressors
- Age <35, <50, <65 years
- D-Dimers median levels
- Fibrinolysis shutdown (by TEG or ROTEM)
- Fibrinogen median levels
- Prone/supine positioning
- Requirement of re-bolusing of alteplase
- Received dose of alteplase as premature death or adverse event or other reasons may preclude the administration of complete treatment
- Elimination of centers contributing <2 cases.

Additional subgroup analyses may be defined at an interim analysis and will be added for the subsequent interim analyses. This will be documented by filing another version of this SAP with the IRBs, DSMB, funder and FDA.

#### **6.6. Missing data**

Missing data are expected to be minimal. If less than 15% and non-differential between study groups, we will proceed with analyses of complete data. If  $\geq 15\%$  or differential between groups (possibly missing not at random), we will add two strategies to the complete dataset analyses:

- 1) Multiple imputation by chained equations (MICE): although MICE is better for missing at random data, we will attempt to use this method.
- 2) Sensitivity analyses: we will assume worst and best clinical scenarios and compare the results with the complete dataset.

### **7. Assessment of safety timing and methods and cessation methods**

#### **Specification of Safety Variables**

Safety assessments will consist of monitoring and reporting adverse events (AEs) and serious adverse events (SAEs) per protocol. This includes any AE, defined as **any unfavorable and unintended sign (including an abnormal laboratory finding), symptom, or disease temporally associated with the use of an investigational medicinal product (IMP) or other protocol-imposed intervention, regardless of attribution.**

This protocol is limited to infusion of two IMPs, alteplase and heparin and blood sampling; thus given their relative short half-life of infusion drugs alteplase (<72 minutes) and heparin (<90 minutes), any effect listed below manifesting within 3 hours of administration of the intervention drugs would be considered potentially temporally related to the intervention drugs. Adverse events associated with blood sampling are considered temporally related if happening within 30 minutes of the sampling.

### Safety check assessments: methods and timing

Serious adverse events and frequency of safety checks are as follows:

Adverse Events	Method for safety check	Safety check frequency	Cessation rule *
Death	NA	NA	NA
Cardio-pulmonary arrest	NA	NA	Any cardio-pulmonary arrest
Allergic reactions including angioedema	Clinical exam	Clinical exam pre, during and immediately post alteplase infusion; every 6 hours post alteplase infusion up to 24 hours; at least every 24 hours after alteplase infusion during heparin infusion or more frequently if any abnormality detected.	Any allergic reaction
Worsening of neurological function	Clinical neurological exam and imaging if applicable per care provider's decision. Most patients will use GCS without verbal component	Clinical exam pre, during and immediately post alteplase infusion; every 6 hours post alteplase infusion up to 24 hours; at least every 24 hours after alteplase infusion during heparin infusion or more frequently if any abnormality detected. Imaging per attending's discretion.	GCS decrease of $\geq 2$ points or focal deficit within 24 hours of study drug infusion or new hemorrhage on CT-Scan or MRI
Worsening of pulmonary function	Arterial blood gas and ventilation indices		$\geq 30\%$ P/FiO 2 baseline reduction
External bleeding	Clinical exam	Clinical exam pre, during and immediately post alteplase infusion; every 6 hours post alteplase infusion up to 24 hours; at least every 24 hours after alteplase infusion during heparin infusion or more frequently if any abnormality detected.	Unresponsive to compression
Gastro-intestinal (GI) bleeding	Clinical exam and hemoglobin	Clinical exam pre, during and immediately post alteplase infusion; every 6 hours post alteplase infusion up to 24 hours; at least every 24 hours after alteplase infusion during	Hemoglobin reduction $> 3\text{g/dL}$ within 24 hours of study drug intervention or requiring RBC transfusion with suspected GI

Serious Adverse Events	Method for safety check	Safety check frequency	Cessation rule *
		heparin infusion or more frequently if any abnormality detected. Endoscopic exam per attending's discretion.	bleeding
Hemoptysis	Clinical exam	Clinical exam pre, during and immediately post alteplase infusion; every 6 hours post alteplase infusion up to 24 hours; at least every 24 hours after alteplase infusion during heparin infusion or more frequently if any abnormality detected. Endoscopic exam per attending's discretion.	Persistent hemoptysis for $\geq 4$ hours or compromising airway
Hematuria	Clinical exam	Clinical exam pre, during and immediately post alteplase infusion; every 6 hours post alteplase infusion up to 24 hours; at least every 24 hours after alteplase infusion during heparin infusion or more frequently if any abnormality detected. Endoscopic exam per attending's discretion.	Persistent hematuria for $\geq 4$ hours or urinary obstruction
Retroperitoneal bleeding		Clinical exam pre, during and immediately post alteplase infusion; every 6 hours post alteplase infusion up to 24 hours; at least every 24 hours after alteplase infusion during heparin infusion or more frequently if any abnormality detected. Endoscopic exam per attending's discretion.	Hemoglobin reduction $>3\text{g/dL}$ within 24 hours of infusion of study drug infusion or requiring RBC transfusion
Tube thoracotomy	Clinical exam and Hgb	Clinical exam pre, during and immediately post alteplase infusion; every 6 hours post alteplase infusion up to 24 hours; at least every 24 hours after alteplase infusion during	Hemoglobin reduction $>3\text{g/dL}$ within 24 hours of infusion of study drug infusion or requiring RBC transfusion

Serious Adverse Events	Method for safety check	Safety check frequency	Cessation rule *
		heparin infusion or more frequently if any abnormality detected.	
Any of the below listed exclusion criteria developing during or up to 3 hours after alteplase or heparin infusion, except for fibrinogen, for which we will set cessation cutoff at 300mg/dL **	Clinical exam and laboratory		Any of listed exclusion criteria developing during or up to 3 hours after alteplase or heparin infusion, except for fibrinogen, for which we will set cessation cutoff at 300mg/dL

\*criteria or attending's decision

\*\* criteria: Acute myocardial infarction; Acute Renal failure (escalating renal failure with creatinine >3 times baseline); Liver failure (escalating liver failure with ALT> 3 times baseline); Cardiac tamponade; Bacterial endocarditis; Severe uncontrolled hypertension defined as SBP>185mmHg or DBP>110mmHg; Seizure; Placement on ECMO; Major surgery required; Requirement of lumbar puncture; INR > 1.7; Platelet count < 100 x 10^9/L or history of HITT; Fibrinogen < 300mg/dL

**8. Dataset availability:** a de-identified dataset will be made available to other investigators who may submit proposals to the PI for additional analyses or validation.

